15.0 Potential Benefits to Subjects*

This study includes assessment and monitoring of medication adherence and behavioral functioning. An assessment of these areas is considered standard of care for individuals infected with HIV, but is not always easily available in clinical settings. Thus, this study has the potential to provide participants (and their care providers, with participant permission) with clinical data that may be valuable in monitoring effects of HIV and its treatments.

Sub-Study:

Subjects do not receive any direct benefits for participating in this sub-study.

16.0 Data Management* and Confidentiality

Data Management and Data Quality. The first randomization involves allocation to CPS vs. SMS using a 1:1 allocation ratio. This step will use stratified randomization in permuted blocks to achieve balance in distribution of behaviorally and perinatally infected youth. The REC data team will program the randomizer in Qualtrics and will not participate either in the intervention delivery or in the adherence reinforcement steps. The protocol team will monitor race, ethnicity, and gender to ensure balanced distribution at the first stage. After 6 months, stratified randomization will occur with permuted blocks within each trajectory. Since second stage randomization is dependent on first stage response status, we will only maintain the balance within each first stage treatment outcome when randomizing at the second stage.

Following the Analytic Core's (AC) standard quality assurance, including checking for outliers and abnormal values using graphical methods, we will verify that the distributions of measures meet the assumptions of the statistical tests to be used, applying a formal test such as the Shapiro-Wilk's test [60]. Transformations will be used when distributional assumptions are not fulfilled. Tests will be conducted to identify potential relationships among baseline demographic and clinical variables and our dependent variables and to see whether they are balanced between groups. If a baseline variable is not balanced between groups and is correlated with the dependent variable ($r > .30$), we will include this variable as a covariate in subsequent analyses. Since we will test more than one primary hypothesis with one primary outcome variable (VL suppression), the Hochberg step-up multiplicity adjustment will be used with a two-tailed family wise alpha-level of .05 [61]. All other tests described below will each have a two-tailed alpha-level of 0.05. Outcome analyses will be based on the principle of intention-to-treat [62].

Quantitative Analysis Plan. The AC's primary analysis will be a comparison of the VL suppression rate (primary outcome) between the CPS and the SMS group at the first stage of randomization (see Study Design). This will be performed using an χ^2 test. We will also compare the drop in VL (measured in logarithmic scale with base 10) between the two groups. Since this is a continuous measure, we will use two-sample t-test to conduct this analysis. We will also compare medication adherence rate (secondary outcome) between the two groups using an χ^2 test. All the primary analyses will be based on initial assignment to groups, using the intention-to-treat (ITT) principle. Each of the primary hypotheses will be tested using linear mixed-effects (LMEs) regression analyses [63]. For testing primary hypothesis 1, the model will include up to 4 repeated assessments of VL suppression (months 0, 3, 6, 12) as the dependent variable. For primary hypothesis 2, we will only focus on non-responders (for both CPS and SMS at stage 1) and compare the VL suppression as dependent variable using a repeated measure LME (months 0, 3, 6, 12). Each LME model will include a random intercept and slope and fixed effects for adherence intervention group, and time, as well as the stratification variables: clinical site, age, gender. A likelihood ratio test will examine the incremental contribution of the group by time interaction, which represents the interaction of interest for Primary Hypothesis 1 and Primary Hypothesis 2, testing for a differential adherence intervention effect over time. The decision rule for each primary hypothesis calls for

PROTOCOL TITLE: ATN 144 SMART

rejection of null hypothesis if this interaction is statistically significant using the Hochberg's step-up alpha adjustment [61]. A site by group interaction will be also examined and included in each model (above) if significant at the .05 level. In addition, likelihood ratio tests will be used to compare the model fit with that having a first order autoregressive (AR1) covariance structure, as described by Hedeker and Gibbons [63].

We will also conduct similar models as above however predicting adherence to ART (secondary outcome), which is measured at every time point. Each model will be a two-level model in which time points (Level 1) are nested within participants (Level 2). This approach accounts for the non-independence of repeated measurements within individuals. The purpose of the LME based [64] analysis for the primary aim is to determine which of the first-stage intervention, CPS or SMS, is associated with the most improvement in VL and adherence, regardless of which second-stage treatment participants received. Also note in SMART design, we compare combinations of subgroups (as in two Specific aims), but not individual subgroups. The study is designed and powered to test the two primary hypotheses with one primary outcome. However, we expect that data based on SMART design will yield valuable information for hypotheses generation involving high quality embedded interventions, which can guide the design of subsequent confirmatory studies.

SMART Secondary Aims. The first of the secondary aims is to compare the effect of tapering with termination at the second randomization among those who received CPS and those who received SMS and achieved VL <200 copies/mL. The AC will compare viral suppression rates among the two groups (tapering vs. termination), followed by more refined analysis using LME modeling. We will first perform a χ^2 test between the two viral suppression rates, followed by mixed-effects modeling.

The purpose of the second secondary aim is to determine which of the adaptive intervention arm leads to the greatest improvement in VL and adherence over the entire study period. To perform this, we will estimate the viral suppression and adherence rates following each of the 8 embedded interventions, and conduct a χ^2 test. Since both responders and non-responders are re-randomized, there is no need to use inverse-probability weighting [65]. However, in order to account for the correlation induced by subjects shared between any two embedded interventions, we will use robust (sandwich) standard errors as in the generalized estimating equations approach [66].

Additionally, we will study the moderators of treatment effect. This is a potentially impactful goal, given the gradual but assured paradigm shift in behavioral interventions from “one-size-fits-all” approach to the modern personalized medicine. Potential moderators in the current context are subject’s demographics and the level of motivation – these can be incorporated in the analysis of the SMART data to deeply personalize the adaptive intervention for future patients. Because of the two-stage nature of the adaptive interventions, a straightforward regression analysis including potential moderators in the model as interaction terms is not suitable due to the possibility of unmeasured confounding induced by selection bias (also known as “collider-stratification bias”) that can be present in time-varying settings, even in presence of randomization [67]. To avoid

PROTOCOL TITLE: ATN 144 SMART

this bias, one needs to employ 2 separate regressions corresponding to the 2 stages of SMART, and carefully move backward through the stages; such a state-of-the-art approach is known as Qlearning [68]. Each regression will contain interaction terms between the stage-specific treatments and the appropriate stage-specific moderators. If any come out significant, then patient characteristics can be used to deeply tailor the interventions for future patients. This will be performed using the R software package qLearn [69]. As customary, secondary aims are not powered and exploratory in nature.

Site Clustering Effects. Although some of the participants will be recruited via a site referral, we do not anticipate substantial site effects. A group identifier for each participant will be included in the merged analytic dataset, and the intra-class correlation (ICC) for each outcome within sites will be calculated prior to conducting multivariate analysis. If no significant variance (<0.05) is carried at the group level, we will reduce the model to a traditional two-level model (only clustering due to repeated measure). If significant group-level variance does emerge, dummy codes to control for site-specific variance will be used to enhance statistical power using a 3-level LME model. In other words, ICC will be included in the model at three-level to control for the clustering effect by design, provided third level is significant. The significance test is always at 0.05. We did not recommend a three-level model all the time as power analysis is conducted considering two-level models only i.e. ignoring site effect.

Sample Size and Power. Statistical power analyses examined the sample size requirements to detect greater than chance group differences on primary outcome (Primary Hypotheses 1 and 2). Because two primary hypotheses have been proposed, the Hochberg alpha adjustment will be used in hypothesis testing. The smaller of those sequential alpha-levels of $.025 (=0.05/2)$ was used in our estimates of the multiplicity-adjusted sample sizes. Preliminary data have traditionally been used for this purpose, but the small sample of the pilot data to provide estimates that are too imprecise for sample size calculations [70]. The power analyses examined the sample sizes required to detect clinically meaningful group differences in the VL suppression rate over time (i.e., the slope). Statistical power was estimated in a Monte-Carlo simulation study using SAS PROC MIXED over 1000 iterations. This represents the differential course for the two interventions over time. Based on the results, the protocol requires recruitment of 190 participants ($\approx 95/\text{group}$ at 1st stage) with $\approx 50\%$ non-responder in 2nd stage. The power table above shows the statistical power to detect standardized interaction effects of various magnitudes (0.45 to 0.55) for the Ns and a two-tailed alpha-level of 0.025. The intra-class correlation coefficient within subjects varied (ICC: .30, .40, .50, based on pilot data). The sample size of 95/group provides sufficient statistical power to detect differences in slopes that results in endpoint differences of $.45 \text{ sd. units}$ with $\text{ICC}=.30$ or .40 and 0.50. In the power analysis it is assumed about 50% responder state at the end of stage 1, thus resulting about 95 subjects in responder and non-responder group.

Strategies for Attrition. Attrition introduces bias and reduces power, precision and generalizability [71]. In keeping with the Intent-to-Treat principle we distinguish between intervention and study termination (complete withdrawal). Accordingly, we will make every effort to continue assessments for the entire course of randomized intervention,

PROTOCOL TITLE: ATN 144 SMART

even among those who do not continue with randomized group [72]. The mixed-effects models will incorporate all available data, even from subjects who do not complete the study. Mixed-effects models yield valid inferences assuming ignorable attrition [73]. For conducting descriptive and two-group comparison Multiple Imputation will be used to replace missing values in the outcomes and other measures. Point estimates, standard errors, and all tests will be calculated using Rubin's rules for combining the results of identical analyses performed on each of the imputed data sets [74].

Additional Secondary Aims. Self-management model analysis will be conducted based on the exploration, preparation, implementation, sustainment (EPIS) model. For the implementation aim, we will explore provider perceptions of the centralized implementation intervention and of the intervention as an evidence-based practice, through qualitative interviews and quantitative assessments based on the EPIS model. Data coding and analysis will proceed in a three-phase process with the EPIS Team. First, consistent with Morgan's [75] recommendations for qualitative content analyses and Hsieh and Shannon's [76] directed qualitative content analytic approach, standard definitions of the concepts to be coded in the text will initially be developed by the ISC based on the EPIS model. We will first systematically review each interview at each time point for all thematic mentions of EPIS model constructs, initially using existing theory to guide categorization, but also allowing themes to emerge from the data through open coding procedures [77, 78]. This combined inductive and deductive coding approach will allow us to both validate and extend the EPIS framework through our analysis. Revision of our initial coding categories will occur iteratively until we reach saturation in the identification of new codes. During this iterative process, categories and their definitions will be refined and sub-categories of codes consolidated, consistent with an axial-coding process. At this point, we will return to each interview and systematically apply the final, revised set of codes. In addition, case codes will be applied to each interview to reflect clinic role, site, cluster, and relevant demographic characteristics of the respondent. All coding will be conducted using NVIVO Version 10. For reliability, a random selection of 30% of the interviews will be independently coded. Coding will be monitored to maintain a kappa coefficient of .90 or higher [79, 80]. Any discrepancies will be discussed and resolved. We will work closely with the EPIS team and then ISC to develop an Intervention Profile and Implementation Resources for replication and sustainment of the intervention. The Profile will synthesize intervention components and implementation analyses into intervention-specific practical guidance for further scale up. Additional resources to facilitate uptake, quality implementation, and sustainment of effective interventions are described in the ISC.

Cost-Effectiveness Analysis Plan. Detailed resource use for the interventions will be collected for the initial randomization and subsequent treatment assignment. These data will be assigned standard cost weights developed by the AC for the purpose of performing incremental cost effectiveness analyses across studies. The use of resource use measures with standard cost values will assure that the economic analyses associated with the clinical trial meet the International Society for Pharmacoeconomics and Outcomes Research (ISPOR) Good Practices for Economic Evaluation Alongside Clinical Trials [81]. We will use a modification of the approach described by Kim and

PROTOCOL TITLE: ATN 144 SMART

colleagues (2015) and used in the economic evaluation of the Positive Charge multisite program aimed at linking HIV-infected youth to care in five states [82]. Data collection will be completed for this component by having each site's financial management contact fill out a standard Excel spread sheet which contains resource use categories relevant to calculation the cost of the intervention. The personnel cost data collected through this method will be combined with study contract and expenditure records to estimate the cost of the CPS and SMS conditions. The personnel data are collected using a standardized Excel spreadsheet to estimate the economic cost of alcohol and other drug treatment programs (e.g., personnel, facilities, supplies). Client case flow data is incorporated to determine the average weekly and annual cost/client for each service type, average cost per intervention episode, and marginal cost per contact. We will also collect data on resources used for tapering and incentives, which will be factored into calculating costs of the interventions. Data on sexual activity will be collected to be used with recent national estimates [54] of cost per HIV infection avoided, and/or on cost per HIV-infection delayed, a more conservative measure. This will allow the estimation of potential cost savings in reduction in new HIV infections. If warranted by study findings, we will use a previously validated Markov decision analysis model [83] to estimate the expected treatment cost savings resulting from the increase in time with suppressed VL. The resource use measures and cost data collected will be used to develop budget impact scenarios to help inform “scale up” and diffusion planning for the most cost-effective intervention combinations.

Intervention Monitoring/Quality Control. It is critical to maintain consistency in the intervention delivery for all participants across all phone calls and the AFs at the REC. As previously described, the AFs will be trained to carry out the intervention. A fidelity evaluation will be conducted to assess whether the AF is collecting the correct information and providing an appropriate level of support. This is to ensure fidelity to intervention delivery and to detect areas of the AF training that need to be improved. A Clinical Coordinator will conduct this fidelity evaluation.

All intervention phone calls between the AF and participant in this study will be digitally recorded utilizing the amplifier and recorder provided by the REC team. AFs will save all digital recordings in a secure network or review. The Clinical Coordinator will review 20% of all audio files for each AF during the initial three months. The audio files will be randomly selected from all audio files saved by the AFs. If 90% of reviewed files are found to be adherent to the requirements listed above, the Clinical Coordinator will only review 10% of all audio files after the initial three months. The recordings will be assessed for: Adherence to the phone call script;

- Appropriate responses/advice/referrals;
- Centering of participants in discussion;
- Order of content discussed;
- Appropriate length of call

The Clinical Team will share any discrepancies and provide critical feedback to the AFs as soon as possible, and other feedback will be provided during the monthly AF

PROTOCOL TITLE: ATN 144 SMART

meetings. This ongoing feedback process will assist in ensuring the integrity of the intervention.

Documentation regarding follow up with the HIV care provider team will be reviewed to ensure that follow-up activities occurred when needed and follow up was conducted in a timely manner. Quality assurance activities will confirm that data captured on study forms are complete and accurate per source documentation. In addition, source documentation or forms will be compared to the data entered into the database to ensure that they match.

Participants' Confidentiality. All laboratory specimens, questionnaires, evaluation forms, reports, and other records will be identified by a coded number only, to maintain participant confidentiality. All records with personally-identifying information will be kept in a locked, limited access area (such as a locked file cabinet). All computer entry and networking programs will be done with coded numbers only. Clinical information will not be released without written permission of the participant (and parent or legally authorized representative, when applicable), except as necessary for monitoring by the ATN SIU or NICHD.

Certificate of Confidentiality. To further protect the privacy of the study participants, the ATN SIU has obtained a Certificate of Confidentiality from the U.S. Department of Health and Human Services (DHHS). With this Certificate in place, the ATN SIU researchers cannot be forced to turn over identifying information about a study participant in any Federal, State, or local criminal, administrative, legislative, or other proceedings. This Certificate does not prevent a study participant from volunteering to turn over their research information, nor does it prevent researchers from providing research-related information to others when requested by the study participant.

Sub-Study:

Data Management. The CASI data will be entered directly by the participant into Qualtrics. Data will reside on a secure server with firewall protection and SSL encryption. Only the Protocol Leads, Data Management and Statistical Team will have administrator privileges enabling them to download these data. The database, data structure, and data quality will be routinely reviewed by the Data Management and Statistical Team. Data will be downloaded into Dropbox Business account which will be used as the study's file sharing site. Lab Manager and Project Manager will be creating specific folders for the Wayne State Statistician to have access to those folders.

Dropbox provides secure shared folders for storing, sharing, and accessing files across sites. In order to allow others to access Dropbox files, the Lab Manager/Project Manager will deliberately share these folders. These folders will be accessible once an invitation sent by Lab Manager/Project Manager is accepted and Dropbox is installed by the site. Dropbox accounts and folders are password protected. At Dropbox, a dedicated security team using the best tools and engineering practices available to build and maintain Dropbox, and has implemented multiple levels of security to protect and back up files. There is also a two-step verification, a login authentication feature which one can enable to add another layer of security to the account. Other Dropbox users can't see our files in Dropbox unless the Lab Manager/Project Manager deliberately share links to files or

PROTOCOL TITLE: ATN 144 SMART

share folders. Dropbox employees are prohibited from viewing the content of files stored in the Project DABS folder. Employees may access file metadata (e.g., file names and locations) when they have a legitimate reason, like providing technical support. Like most online services, a small number of Dropbox employees will be able to access user data for the reasons stated in their privacy policy (e.g., when legally required to do so). But that's the rare exception, not the rule. Dropbox has strict policies and technical access controls that prohibit Dropbox employee access except in these rare circumstances. In addition, Dropbox employ a number of physical, technical, and heuristic security measures to protect user information from unauthorized access.

Data Quality. Data quality will be examined before statistical analysis can be conducted, including examination of missing data, invalid responses, assessment of distributional assumptions, and identification of outliers.

Data Analysis Plan. To assess the feasibility of using DBS we will examine descriptive data to determine how many participants returned the DBS specimen. Descriptive statistics, frequencies, means and standard deviations, will be used to describe the samples' demographic characteristics as wells as perceptions of their suitability, feasibility and acceptability. To identify potential barriers and facilitators of testing response rates we will conduct exploratory analyses comparing differences in demographics and perceptions in youth who did return the DBS specimen versus those who did not. We will examine proportional differences using chi-square tests for categorical variables and mean differences using t-tests for continuous outcomes ($\alpha = 0.05$). For the suitability, feasibility and acceptability scales we will calculate Pearson correlation coefficients to examine the relationship between these variables and potential barriers and facilitators. Point bi-serial correlations will be used when comparing the scales and dichotomous variables.

Confidentiality. All laboratory specimens, questionnaires, evaluation forms, reports, and other records will be identified by a coded number only, to maintain participant confidentiality. All records with personally-identifying information will be kept in a locked, limited access area (such as a locked file cabinet). All computer entry and networking programs will be done with coded numbers only. Clinical information will not be released without written permission of the participant (and parent or legally authorized representative, when applicable), except as necessary for monitoring by the ATN SIU or NICHD.

To further protect the privacy of the study participants, the ATN SIU has obtained a Certificate of Confidentiality from the U.S. Department of Health and Human Services. With this Certificate in place, the ATN SIU researchers cannot be forced to turn over identifying information about a study participant in any Federal, State, or local criminal, administrative, legislative, or other proceedings. This Certificate does not prevent a study participant from volunteering to turn over their research information, nor does it prevent researchers from providing research-related information to others when requested by the study participant.

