11.0 Local Number of Subjects

We will enroll 120 HIV-positive youth living with HIV aged 15-24.

Sub-Study:

This study aims to enroll 50 YLH, ages 15-24, nationally.

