1.2.4 Sample Size and Power

Sample Size and Power. Statistical power analyses examined the sample size requirements to detect greater than chance group differences on primary outcome (PH1 and Ph2). We have used Susan's formula with a total sample size of 120.

<http://people.seas.harvard.edu/~samurphy/papers/APPProof.pdf>

| Power Table | | | |
|--------------------|------------|------------|-----------------------------|
| ES | p | N | N(10% attrition adjustment) |
| 0.55 | 0.4 | 86 | 96 |
| | 0.5 | 104 | 116 |
| | 0.6 | 130 | 144 |
| | 0.7 | 174 | 192 |
| 0.6 | 0.4 | 74 | 80 |
| | 0.5 | 88 | 98 |
| | 0.6 | 110 | 120 |
| | 0.7 | 146 | 160 |

Alternatively, for the two groups comparison this corresponds to n=60/group. This sample size is sufficient to provide 80% power (or more) for a standardized Effect Size (ES) of 0.55 or more, using a t-distribution for a two tailed test with $\alpha=0.05$, with 10% attrition assuming equal responder rate (p) in both arms.

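### The protocol's power section still rests on 190 participants and a 0.45 SD target, although enrolment is set at 120; the SAP re-powers for 120 only by using a larger effect and a looser alpha

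*Protocol*

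**What the plan says.** Protocol section 16.0, under Sample Size and Power, states that "the protocol requires recruitment of 190 participants", about 95 per group at stage 1, with roughly half expected to be non-responders. It adds that "The sample size of 95/group provides sufficient statistical power to detect differences in slopes" producing an endpoint difference of 0.45 SD, for within-subject correlations of 0.30 to 0.50 and a "two-tailed alpha-level of 0.025". The method is a simulation of slopes. The power table it mentions is not in the readable text, and no power percentage is printed.

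Protocol section 11.0 states "We will enroll 120 HIV-positive youth living with HIV aged 15-24". The Study Summary and sections 12.0 and 24.0 give the same 120.

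SAP section 1.2.4 works "with a total sample size of 120", that is 60 per group. It claims at least 80% power for a standardised effect of 0.55 or more, two-sided alpha 0.05, with 10% attrition.

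On alpha, SAP section 1.1 prescribes Hochberg at a family-wise 0.05. Section 1.2.1 uses Hochberg in its decision rule and then says alpha will not be adjusted, because the sample has shrunk.

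**The concern.** Both sample sizes are current protocol text, so this is not a clash with the amendment log. The sections that fix enrolment carry 120, and the section that justifies it was left at 190. The protocol contains no power statement for 120.

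The power paragraph presents its target as clinically meaningful and as covering both primary hypotheses. Anyone judging the trial's sensitivity from the protocol alone would credit it with a sample 58% larger than planned (190/120 = 1.58). Anyone holding both documents finds two sample sizes, two effect sizes and two alpha levels for the same pair of hypotheses, with nothing to say which governs.

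**Working it through.** **Inputs.** From Protocol section 16.0: 1:1 allocation, 95 per group, d = 0.45, two-sided alpha 0.025, within-subject correlation 0.30 to 0.50, visits at months 0, 3, 6 and 12, and 50% responders. From Protocol section 11.0: 120 enrolled, so 60 per group. From SAP section 1.2.4: d = 0.55, alpha 0.05, and 10% attrition, so 0.9 × 60 = 54 per group. The 80% benchmark for the protocol is an assumption, tested in step 1.

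**1. Reproduce the protocol's 95 per group.** Normal approximation: n = 2(z₁₋α/₂ + z₀.₈₀)² / d² = 2(2.241 + 0.842)² / 0.45² = 93.9, so 94 per group. The noncentral t version gives 95.1. So 95 per group is what an 80% design needs at 0.45 SD and alpha 0.025.

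**2. Power at the planned enrolment (PH1).** Two-sample t-test, noncentrality d√(n/2); for n = 60 and d = 0.45 this is 0.45 × √30 = 2.465.

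| n per group | d | alpha 0.025 | alpha 0.05 |
|---|---|---|---|
| 95 | 0.45 | 0.799 | 0.870 |
| 60 | 0.45 | 0.578 | 0.686 |
| 54 | 0.45 | 0.528 | 0.639 |
| 54 | 0.55 | 0.720 | 0.808 |

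The bottom right cell reproduces the SAP's claim of at least 80%.

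**3. Cross-check on the slope scale.** Assume compound symmetry, unit variance, complete data and no random-slope variance. A 0.45 SD difference at month 12 is a slope difference of 0.45/12 = 0.0375 per month. The visit months have mean 5.25 and S = Σ(t − t̄)² = 78.75. The standard error is √[2(1 − ρ)/(nS)]. For n = 60 and ρ = 0.30 it is √(1.4/4725) = 0.0172, so z = 2.18 and power = Φ(2.18 − 2.24) = 0.475.

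| n per group | alpha | ρ = 0.30 | ρ = 0.40 | ρ = 0.50 |
|---|---|---|---|---|
| 95 | 0.025 | 0.69 | 0.76 | 0.84 |
| 60 | 0.025 | 0.475 | 0.54 | 0.63 |
| 60 | 0.05 | 0.59 | 0.65 | 0.73 |

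At equal alpha the loss from 95 to 60 per group is about 21 or 22 points, the same as in the t-test (0.799 − 0.578 = 0.22).

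**4. Effect detectable with 80% power (t-test, PH1).**

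| n per group | alpha 0.05 | alpha 0.025 |
|---|---|---|
| 60 | 0.52 SD | 0.57 SD |
| 54 | 0.54 SD | 0.60 SD |

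**5. PH2, non-responders only, t-test, before attrition.** At 50% non-response, 190 gives 190 × 0.5 / 2 = 47.5 per arm, and 120 gives 30 per arm.

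| Enrolled | per arm | d | alpha | power |
|---|---|---|---|---|
| 190 | 47.5 | 0.45 | 0.025 | 0.47 |
| 120 | 30 | 0.45 | 0.025 | 0.30 |
| 120 | 30 | 0.55 | 0.05 | 0.55 |

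**The case against.** The best reply is that the SAP has already dealt with this. It does its sums for exactly 120, acknowledges the smaller sample, labels the earlier hypotheses as original, and redefines both the primary outcome and its time point. On that view the protocol paragraph is merely stale. Much of this stands. A reader might infer from the 190-versus-120 mismatch that the trial has no power basis at its real size, and the documents do not support that: the SAP's two-group figure reproduces. But it reproduces only with a larger effect and a looser alpha. Even at alpha 0.05, 60 per group gives 69% for 0.45 SD. Nothing in the SAP withdraws the protocol's target.

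Three further stronger readings should be resisted.

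- **That power is simply 58%.** This holds only at alpha 0.025. SAP sections 1.2.1 (in part) and 1.2.4 point to 0.05, which gives 69%. Until the alpha conflict is settled, the range is the honest answer.
- **That the protocol promises 80%.** It says only that power is sufficient. The 80% is inferred because 95 per group matches it, and the protocol simulated slopes rather than running a t-test.
- **That cutting enrolment to 120 caused the PH2 shortfall.** At 190, PH2 already had about 47% power for 0.45 SD at alpha 0.025. The smaller sample worsens this but did not create it. The 30 per arm also depends on the 50% assumption: Protocol section 5.0 treats participants without a 3-month viral load as non-responders, so the pool could be larger.

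A null result being misread against 0.45 SD is a possible consequence, not a certain one, since a reader of the SAP would see 0.55.

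**Conclusion.** The point holds as an internal inconsistency with a measurable consequence. The protocol's power paragraph describes a trial of 190 that is not being run. For its stated target of 0.45 SD, the planned 120 gives about 58% power at alpha 0.025 or 69% at alpha 0.05 (53% or 64% after 10% attrition). The slope approximation gives 47.5% to 63% at alpha 0.025 before attrition. The SAP supplies a valid 80% statement for the stage-1 two-group comparison at 0.55 SD and alpha 0.05, but that is a different target. Neither document's two-group figure supports 80% power for PH2.

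These figures assume equal groups and 50% non-response for PH2. The t-test figures are an approximation to a simulation whose table cannot be read here. The contradiction between 190 and 120 depends on none of these assumptions.

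**What to change.** In Protocol section 16.0, replace the 190 (95 per group) and 0.45 SD text with the power for 120, consistent with SAP section 1.2.4:

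- **Alpha.** Declare one rule and use it in the power statement and the analysis, resolving the Hochberg conflict between SAP sections 1.1 and 1.2.1.
- **PH1.** State the effect detectable with 80% power: 0.52 SD (alpha 0.05) or 0.57 SD (alpha 0.025) at 60 per group; 0.54 or 0.60 SD at 54 per group.
- **PH2.** State it separately. At 50% non-response and about 30 per arm, power is about 30% at 0.45 SD and alpha 0.025, and about 55% at 0.55 SD and alpha 0.05. Amend the statement in section 16.0 that the study is powered for both primary hypotheses.

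The cost is wording, plus one decision on alpha that should be made without sight of outcomes by arm. Enrolment, procedures and data collection do not change. The stated sensitivity becomes less favourable.
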